Furthermore, no study has conducted thorough measurements of the optics and shape the eye in order to determine how soft bifocal contact lenses may slow myopia progression. Measurement of peripheral defocus with the contact lens on the eye while looking at distance and near will provide a thorough assessment of the refractive error experienced by the eye. Comparison of the treatment effect between varying add powers of soft bifocal contact lens wearers and soft spherical wearers will determine whether the effect is primarily due to changes in eye shape or due to the contact lens itself. If greater peripheral defocus created by stronger add powers leads to differences in treatment effect, the contact lens is the primary determinant of myopia control, whereas if the relationship between peripheral defocus and myopia control is a greater determinant of myopia control than the amount of defocus, then eye shape is the primary determinant of myopia control. In addition to peripheral defocus, this three-year study will also examine the role of accommodative lag, pupil size, peripheral astigmatism, and the most myopic peripheral meridian in order to provide the most thorough assessment ever conducted of the optical profile and its effect on refractive error development.

Determining the role of peripheral defocus on the shape of the eye is also important for understanding how peripheral defocus may alter refractive error. Animal models indicate that hyperopic defocus results in longer eye lengths restricted to the corresponding retinal location. If this is the case in humans, peripheral myopic defocus produces slower peripheral growth than central growth. Comparing the change in both central and peripheral refractive error between soft bifocal and single vision contact lens wearers will help determine whether peripheral myopic defocus results in local changes in ocular shape or uniform changes in eye growth.

[figure not shown]
Data regarding whether greater peripheral myopic defocus slows myopia progression and how peripheral myopic defocus alters eye shape will provide crucial guidance toward optimizing the peripheral defocus signal in future contact lenses designed for myopia control and perhaps prevention of myopia onset. With a three-year randomized clinical trial of 294 myopic children between the ages of 7 and 11 years at baseline, we will accomplish the following specific aims:

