- Specific Aim 1:** to compare the change in myopia between single vision contact lens wearers and soft bifocal contact lens wearers to test the hypothesis that soft bifocal contact lenses slow myopia progression in a dose-dependent manner in children,
- Specific Aim 2:** to determine whether peripheral defocus created by soft bifocal contact lenses is associated with myopia progression to test the hypothesis that peripheral myopic defocus slows myopia progression in children, and
- Specific Aim 3:** to determine whether changes in ocular shape differ between children wearing single vision and soft bifocal contact lenses to test the hypothesis that peripheral myopic defocus globally slows eye growth.

Chapter 4: Study Design

This is a multi-center, randomized clinical trial. Subjects will be randomly assigned to wear single vision contact lenses, soft bifocal contact lenses with a +1.50 D add, or soft bifocal contact lenses with a +2.50 D add for at least three years. Figure 4-1 illustrates the study schedule.

Figure 4-1: Flowchart illustrating the visit schedule and randomization.

Chapter 5: Sample Size

All sample size calculations were performed using PASS 2005 software using $\alpha = 0.05$ and $\beta = 0.10$ (power = 80%). Estimates of sample size were computed for each specific aim.

Specific Aim 1: to compare the change in myopia between single vision contact lens wearers and soft bifocal contact lens wearers to test the hypothesis that soft bifocal contact lenses slow myopia progression in a dose-dependent manner in children

Aim 1 is designed to compare myopia progression between two soft bifocal adds and single vision contact lens wearers using the mean value of the cycloplegic spherical equivalent (sphere + $\frac{1}{2}$ cylinder) as measured at one, two, and three years. These comparisons will be made using the common estimate of error obtained from a three group x three time point repeated measures analysis of covariance (ANCOVA), with the baseline spherical equivalent used as a covariate. To increase the efficiency of the F-tests performed as part of the ANCOVA, the total sample size will be equally allocated between the soft bifocal and single vision contact lens groups.

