Sample size calculations are driven, in part, by the desired difference in spherical equivalent change between the three groups. This difference needs to be of a magnitude that is considered clinically relevant. Sample sizes are based upon the percent reduction in myopia progression between the two soft bifocal contact lens groups and the single vision contact lens group. Data used in the calculations are taken from the single vision contact lens group of the ACHIEVE Study, where the mean (\pm SD) myopia progression was $-1.29 \text{ D} \pm 0.71$ over three years (Walline et al., 2008). If we want to detect a 50% treatment effect (reducing the amount of myopia progression by roughly 0.65 D in the +2.50 D add group) and we estimate that the mean treatment effect for the +1.50 D add group is halfway between the single vision contact lenses and the +2.50 D add group (i.e., reducing myopia progression by 0.30 D in the second add), then the sample size required at 80% power is 24 per treatment group. Estimating the effect of the +1.25 D add group to be halfway between the two groups results in the largest sample size possible (a conservative estimate). Should we find that both adds have a similar effect, we will be more than adequately powered. If we look at a reduction of 0.50 D (a treatment effect of 40% in the highest add group), then the sample size is 40 per treatment group at 80% power. A 30% treatment effect (a reduction of about 0.40 D in the amount of myopia progression in the +2.50 D add group) yields a sample size of 62 subjects per treatment group.

Specific Aim 2: to determine whether peripheral defocus created by soft bifocal contact lenses is associated with myopia progression to test the hypothesis that peripheral myopic defocus slows myopia progression in children

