Analysis of the relationship between the amount of peripheral defocus and the amount of myopia progression will provide information on how the level of peripheral defocus may affect the progression of myopia. That is, are higher levels of peripheral myopic defocus associated with a decreased rate of foveal myopia progression? Peripheral defocus is measured in this study at multiple locations (20°, 30°, and 40°) in two gaze positions (nasal and temporal). The association between peripheral defocus and myopia progression will be assessed using a correlation analysis and linear regression. Based on recent work by Sankaridurg et al. (2011), a clinically meaningful magnitude of correlation between peripheral defocus and myopia progression is 0.25. To detect a correlation as small as 0.25 at 80% power would require 123 subjects total.

Specific Aim 3: to determine whether changes in ocular shape differ between children wearing single vision and soft bifocal contact lenses to test the hypothesis that peripheral myopic defocus globally slows eye growth

Aim 3 is designed to evaluate differences in the change in ocular shape between the two soft bifocal and single vision contact lens groups using the measure of relative peripheral refractive error across the horizontal and vertical meridians of the eye. Relative peripheral refractive error is computed by subtracting the central cycloplegic spherical equivalent autorefraction from the peripheral spherical equivalent autorefraction, each measured with no refractive

error correction. Analyses will use a repeated measures ANCOVA with gaze direction and fixation as within-subject factors. To increase the efficiency of the F-tests performed as part of the ANCOVA, the total sample size will be equally allocated between the soft bifocal and single vision contact lens groups.

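### As written, Aim 2 has no arm term, so the treatment effect alone can produce a pooled defocus–progression correlation; the within-arm slope should be reported beside it

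*Combined protocol and SAP*

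**What the plan says.** Chapter 3 sets Aim 2 "to test the hypothesis that peripheral myopic defocus slows myopia progression in children". The analysis is given only in Chapter 5, under Specific Aim 2: "The association between peripheral defocus and myopia progression will be assessed using a correlation analysis and linear regression". No arm term, stratification, within-arm estimate or other covariate is named, whereas the same chapter describes a repeated measures ANCOVA for each of Aims 1 and 3.

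The target is that "a clinically meaningful magnitude of correlation between peripheral defocus and myopia progression is 0.25", and "To detect a correlation as small as 0.25 at 80% power would require 123 subjects total". One arm has 98 children, so a sample of 123 must draw on more than one arm.

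On the exposure, "Peripheral defocus is measured in this study at multiple locations": three eccentricities in two gaze directions, with no summary measure chosen. Chapter 24 schedules defocus through the lens at distance at Visits 1, 5, 7 and 9. Chapter 15 schedules it at near at Visits 3, 5, 7 and 9.

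Chapter 3 says that distance-centre bifocal lenses give the periphery relatively more myopic defocus than spherical lenses, and it treats stronger adds as giving more of it. Chapter 5, under Specific Aim 1, plans for progression to differ between arms.

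**The concern.** The exposure in Aim 2 is partly set by the randomised lens, and the outcome is the one the lens is expected to change. If the arms are combined without an arm term, the arm with more defocus and slower progression sits at one end of the scatter plot and the control arm at the other. That alone makes a correlation, even if two children wearing the same lens progress alike whatever their defocus.

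A significant pooled correlation could then be little more than the Aim 1 result on another axis, yet be published as evidence of mechanism. Table 6-2 schedules a separate paper on peripheral myopic defocus and progression, so the distinction matters for a planned report.

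**Working it through.** **The plan's own figure.** For one correlation, two-sided alpha 0.05 and 80% power, Fisher's z gives n = ((1.960 + 0.842)/atanh 0.25)² + 3 = (2.802/0.2554)² + 3 = 123.3. With the small bias term it is 122.4, which rounds up to 123. The stated 123 therefore reproduces, as the sample size for a single simple correlation with no covariates.

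**Inputs.** From Chapter 5, Specific Aim 1: SD of three-year progression 0.71 D; reductions in the +2.50 D arm of 0.65, 0.50 and 0.40 D (the 50%, 40% and 30% effects); the +1.50 D arm about halfway; equal allocation. Two assumptions are added. The 0.71 D is the within-arm SD in every arm. A share s of the defocus variance lies between arms; the documents give no value, so a range is shown.

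**Formula.** With no within-arm association and equally spaced arm means, pooled r = √(between-arm share of progression variance) × √s.

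**Between-arm share of progression variance.** Arm means 0, d/2 and d have variance d²/6; the within-arm variance is 0.71² = 0.5041.

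- 50% effect: 0.65²/6 = 0.0704; 0.0704/0.5745 = 12.3%; square root 0.350
- 40% effect: 0.50²/6 = 0.0417; 0.0417/0.5458 = 7.6%; square root 0.276
- 30% effect: 0.40²/6 = 0.0267; 0.0267/0.5308 = 5.0%; square root 0.224

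These square roots are the largest possible pooled r (s = 100%). The share needed to reach 0.25 is (0.25/0.350)² = 51% at the 50% effect and about 82% at the 40% effect. At the 30% effect it would exceed 100%, so 0.25 is out of reach.

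**Pooled r, and chance of p < 0.05 with 267 children (Fisher z), when the within-arm link is zero**

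| s | 50% effect | 40% effect | 30% effect |
|---|---|---|---|
| 10% | 0.11; 44% | 0.09; 30% | 0.07; 21% |
| 50% | 0.25; 98% | 0.20; 90% | 0.16; 74% |
| 75% | 0.30; >99% | 0.24; 98% | 0.19; 89% |

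With 123 children and s = 50%, the chances are 79%, 58% and 42%. Simulation (4,000 runs per setting, s = 50% and 75%) agrees. Spacing defocus as 0, 1.50 and 2.50 D, or using the plan's 0.30 D for the middle arm, changes r by less than 0.005.

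**With arm in the model.** In the same simulations rejection returns to about 5% (4.5% to 5.5%). A partial r of 0.25 needs about 126 children.

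**Precision of the within-arm slope.** Suppose instead that defocus acts with one common slope and that this gives a pooled r of 0.25. With both variables standardised, the residual variance is 1 − 0.0625 = 0.9375, and partial r = 0.25√(1 − s)/√(0.9375 + 0.0625(1 − s)).

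- s = 50%: 0.1768/0.9843 = 0.18
- s = 75%: 0.1250/0.9763 = 0.13

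At 264 completers (90% of 294), with two arm terms, √(264 − 5) = 16.09. Power is Φ(0.1816 × 16.09 − 1.96) = 83% and Φ(0.1287 × 16.09 − 1.96) = 54%.

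**The case against.** **The arm term is unstated, not excluded.** A reader might infer that the plan commits to a regression without arm. It does not: the covariates are simply not given, and Chapter 31 has a detailed analysis plan drawn up with the coordinating centre when a paper is approved. This stands as a limit on wording. It does not remove the gap, because a key covariate left open until then is not pre-specified here.

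**The between-arm signal is not an artefact.** Aim 2 concerns defocus created by the lenses, and the between-arm part is the randomised part of that exposure. Adjusting for arm leaves differences among children, open to confounding by eye shape, pupil size or lens centration. This stands. A reader might conclude that only the within-arm slope can support the hypothesis; the documents do not support that, and the two slopes answer different questions.

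**Chapter 3 does not assign the separation to this correlation.** The statement that something "will determine whether the effect is primarily due to changes in eye shape or due to the contact lens itself" has as its subject the comparison of treatment effect across add powers. It would be too strong to say that Aim 2's correlation was meant to do that job. The next sentence of Chapter 3 does, however, weigh the defocus–control relationship against the amount of defocus, and no stated analysis separates them.

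**Multiplicity.** A reader might infer six tests, each at 0.05. No testing rule is stated, so an error rate built on one would be conjecture; enrolment is in any case set by the 267 for Aim 3. What remains is that no defocus summary is named.

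**A narrower sample.** If Aim 2 used only the two bifocal arms, which Chapter 5 does not say, arm differences alone would give at most about 0.22 to 0.24 at the 50% effect.

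**Conclusion.** The concern holds in a limited form. As written, Aim 2 combines arms with no arm term, and on the plan's own Aim 1 figures the treatment effect alone can yield a pooled correlation that is often significant. A significant pooled r is compatible with the defocus hypothesis, but by itself it cannot separate defocus from any other effect of the assigned lens.

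A reader might infer that the treatment effect will by itself deliver the target of 0.25. The documents do not support that: it depends on the effect size and on an unknown between-arm share, and 0.25 cannot be reached at the 30% effect. Over shares of 10% to 75%, the chance of a significant pooled test runs from about 21% to over 99%. The result also rests on treating 0.71 D as a common within-arm SD. Aim 1 and the enrolment target are unaffected.

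**What to change.** Keep the pooled correlation. Add a linear regression of three-year progression on one pre-named defocus summary, with arm and baseline spherical equivalent in the model. State which locations the summary combines, whether viewing is at distance or near, and which visit supplies it. Report the within-arm slope beside the pooled slope. Do not describe a pooled association alone as evidence of a defocus effect beyond lens assignment.

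The cost is one extra model and a few sentences; no new data are needed. The drawback is that the within-arm slope is observational and uses a narrower range of defocus. At the larger between-arm share a true common slope would be missed nearly half the time, so a null within-arm result should be reported with its confidence interval and not read as evidence against the mechanism.

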Sample size estimates are based upon a magnitude difference of the change in “ocular shape” between the single vision contact lens and the +2.50 D add bifocal treatment groups of 0.40 D. In order to ensure that we have adequate sample size to find a true difference, we have made the assumption that the +1.50 D add bifocal group will experience a change that is intermediate between the other two groups (i.e., 0.20 D). Making this assumption gives us a conservative estimate of sample size (i.e., the maximum sample size). While no longitudinal data assessing the amount of change in periphery that can be considered clinically meaningful, it is reasonable to assume that a clinically meaningful change in the center would be considered a clinically meaningful change in the periphery as well. As such, we know that the minimal difference in central refractive error change that has been detected in previous studies is 0.13 D over one year. If this amount of difference in refractive error change continues for three years, then the minimal meaningful difference would be 0.39 D, which we rounded to a 0.40 D difference. The standard deviation arises from the Study of Theories about Myopia Progression, and is set at 0.85, which represents the most conservative standard deviation in the change in relative peripheral refraction seen across measures. Using this information the sample size required to detect this magnitude of difference in the change in ocular shape between treatment groups with 80% power is 89 subjects per group, for a total sample size of 267 subjects.

Sample Size Conclusion

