Table 5-1 provides a summary of the sample size requirements based on the three study aims. Although we strive to retain all subjects, the sample size will be adjusted to account for a possible 10% loss to follow-up. This is a reasonable expectation. [name], when at Ohio State, had a retention rate of 98% in his Study of Theories about Myopia Progression clinical trial, and other clinical vision studies conducted at the University of Houston have retention rates exceeding 90%. Likewise, [name] experiences at Ohio State with ACHIEVE (OSU clinic saw 100% of subjects for final visit) and the Contact Lens and Myopia Progression trial (100% of subjects at final visit) indicate that a 10% loss to follow-up is an acceptable assumption. Using the maximum sample size from Table 5-1 (n=267) and adjusting for 10% loss to follow-up gives a **total sample required of 294** (98 children assigned to each treatment group).

Table 5-1: Total sample size required at 80% power in the Soft Bifocal Contact Lens Myopia Control Study

| Aim | Total sample |
|----------------------|--------------|
| Specific Aim 1 | |
| 50% treatment effect | 72 |
| 40% treatment effect | 120 |
| 30% treatment effect | 186 |
| Specific Aim 2 | 123 |
| Specific Aim 3 | 267 |

Chapter 6: Timeline

During the first six months of funding, preparation for the trial will begin. The DSMC will meet as early as possible (after preparation of study forms and DSMC binders) in order to finalize the protocol. Once the protocol is finalized, certification of examiners will begin at the FIG meeting, both near the end of the initial six-month period.

Recruitment will begin at the beginning of month seven and continue for 15 months. All follow-up visits will begin within one week of the first subject visit. The last one-year, two-year, and three-year visits are expected to be complete within one month of the anniversary date of the last subject enrolled.

The DSMC will meet annually, after recruitment and each year of follow-up is complete and the data are analyzed. FIG meetings will be held after each DSMC meeting in order to update protocols, motivate investigators, and discuss problems encountered. Writing groups will also meet during the FIG meetings.

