For example, if a subject does not want to wear contact lenses, the subject should be asked why s/he does not want to wear contact lenses and every effort should be made to alleviate the reason for discontinuation. The subject and parent should be reminded of the importance of continuing in the study and reminded of the free comprehensive eye examinations and glasses throughout the study. At each follow-up visit, the subject should be asked if s/he would like to resume contact lens wear. If there are any irregularities in the case or if there are questions, contact the Study Chair.

Discontinuation

Subjects have the right to withdraw participation in a study at any time, but losses to follow-up may significantly affect the validity of the study. Every effort should be made to retain every subject for the entire study, including subjects who are difficult to schedule, subjects who are very demanding, and subjects whom you simply do not like.

If a subject moves from the area, the subject may be examined at the other clinic site or the Chair's Office may pay for the subject and one adult to fly to an appointment, one night's stay in a hotel, and ground transportation. The total reimbursement should not be greater than \$1350 per visit. This decision will be made on a person-by-person basis by the Clinic PI and Study Chair.

If a subject cannot be located, and the clinic site has exhausted all potential contacts, the Chair's Office will conduct a professional search using alternative resources. Contact the Chair's Office as soon as the clinic site determines that they are not able to locate the subject.

If a subject wishes to discontinue and all alternatives have been discussed, the examiner should ask the subject if he or she would come back for Visit 9 only. If the subject agrees to return for the last visit, then he or she is not a loss to follow-up, and the Discontinuation Form should not be completed. If the subject refuses to attend all of the remaining visits, the Discontinuation Form should be completed. At this time, complete the discontinuation section of the Study Completion Form in REDCap. Ask the subject if it would be acceptable to continue sending them information and see if it would be okay to call them before the last visit to determine whether the subject changed his or her mind.

Chapter 10: Informed Consent

Introduction

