 15. Exit the EyeSuite application when done with measurements. Say **No** to Database Backup (it will take about 30 minutes). Shut down the computer using the Microsoft logo in the bottom left corner of the screen.
- * Any reading on the Lenstar that is highlighted in red is not valid. Readings highlighted in red must be deleted and, if possible, replaced with a valid reading. If it is not possible to obtain five valid readings for a measurement location, a protocol deviation form should be completed, documenting that readings highlighted in red were deleted and could not be replaced with valid ones.

Data Download

Data should be downloaded from Lenstar weekly. We cannot choose the data to be downloaded so all data stored on the Lenstar must be downloaded each time. A template with the name CSV_BLINK is provided to guide the export.

1. Place a USB drive in the USB port on the hard drive of the Lenstar and open EyeSuite.
2. Click on **Tools**, then **Reporter**.
3. In the **Template File:** box, enter C:\Users\LenStar\Documents\Templates\CSV_BLINK.txt and click **Next**
4. In **Report File:**, enter C:\Users\LenStar\Documents\BLINKOutput\clinic.MMDDYY.csv (date is date of download)
 - Example: C:\Users\LenStar\Documents\BLINKOutput\OSU.041714.csv
 - Example: C:\Users\LenStar\Documents\BLINKOutput\UH.110914.csv
5. Click Next. The Lenstar will give you a prompt that the report was generated successfully.
6. Click Exit
7. In REDCap under Applications, select File Repository.
8. Choose upload new file. Select the file, and upload into the repository. The OCC will download from the File Repository once a week, and remove it from the repository so the data do not remain accessible.

Chapter 22: Peripheral Refractive Error Without Contact Lens

Performed By

Masked Examiner

Eyes

OD

Equipment

Peripheral refractive error will be measured using the Grand Seiko WAM-5500 Binocular Autorefractor/Keratometer (AIT Industries, Bensenville, IL).

Reason for Measuring

Peripheral refractive error without a contact lens is a surrogate for shape of the eye. Most longitudinal myopia studies have used peripheral refractive error as a measure of eye shape. Peripheral refractive error will be measured using the Grand Seiko WAM-5500 Binocular Autorefractor/Keratometer along the horizontal and vertical meridian of the eye. All Grand Seiko settings and laptop computer settings are the same as noted in the *Central Autorefraction* chapter.

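### The repeated-measures ANCOVAs for Aims 1 and 3 come with no missing-data rule; as ordinarily fitted they drop incomplete children, which risks selection in Aim 1 and uses up a reserve that Aim 3 hardly has

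*Combined protocol and SAP*

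**What the plan says.** **Aim 1 (Chapter 5, Specific Aim 1).** Myopia progression at one, two and three years is compared with a "three group x three time point repeated measures analysis of covariance (ANCOVA), with the baseline spherical equivalent used as a covariate".

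**Aim 3 (Chapter 5, Specific Aim 3).** For relative peripheral refractive error, "Analyses will use a repeated measures ANCOVA with gaze direction and fixation as within-subject factors". Time is not listed as a factor. Chapter 22 gives ten peripheral locations without a lens: six horizontal and four vertical.

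**Allowance (Chapter 5, Sample Size Conclusion).** Aim 3 gives the largest requirement, 89 per group or 267 in all, and "the sample size will be adjusted to account for a possible 10% loss to follow-up". The result is 294, or 98 per group. The support offered is retention and final-visit attendance in other studies.

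**Who is retained (Chapter 9, Discontinuation).** A child who wishes to stop is asked to come back for Visit 9 alone. "If the subject agrees to return for the last visit, then he or she is not a loss to follow-up".

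**Missing data.** The text supplied states no statistical handling of missing visits or locations, no analysis set and no expected rate. Chapter 29 describes data-entry checks only. Chapter 22 asks for at least five acceptable readings at each location and names no fallback. Chapter 21 does foresee failures in the companion eye-length series: "If it is not possible to obtain five valid readings for a measurement location, a protocol deviation form should be completed".

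**The concern.** A classical repeated-measures ANCOVA works on complete rows. In Aim 1 a row is the three annual values. In Aim 3 it is every gaze location, and because the outcome is a change, both a baseline and a follow-up value at each. One gap removes the whole child.

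This collides with the retention rule. Sites are told to work for a Visit 9 from children who would otherwise leave, and those children count as retained. A child who stopped before completing Visits 5 and 7 would then be removed from the primary analysis. A child who attended Visits 5 and 7 and then left would lose both of those values too. Membership of the Aim 1 comparison would depend on attendance after randomisation, so it would no longer compare all randomised children.

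In Aim 3 the issue is number. The 10% allowance is for loss to follow-up. A child who attends but lacks one location is not counted in it, and this is the aim that fixes the trial size.

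**Working it through.** **1. Reproduce the plan's figures.** Inputs from Chapter 5: alpha 0.05 and 80% power (beta is printed as 0.10, but the sample sizes match 80%). Aim 3 differences are 0, 0.20 and 0.40 D with SD 0.85. Aim 1 has SD 0.71. The test is the three-group F-test with noncentrality λ = n × Σ(mean − grand mean)² / SD².

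- Aim 3: Σ = 0.04 + 0 + 0.04 = 0.08, and 0.08/0.85² = 0.1107. With n = 89, λ = 9.86 and power is 80.5%. This matches 89 per group.
- Aim 1, effects of 0.65, 0.50 and 0.40 D: 24, 40 and 62 per group. All match Table 5-1.
- Inflation: 267 × 1.10 = 293.7, so 294. (267/0.90 gives 297, a difference of 3 children.)

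**2. Reserve in Aim 1.** The largest requirement is 186, and 1 − 186/294 = 36.7% could be dropped. For the 0.40 D effect, power is 90.9%, 89.1% and 84.3% if 15%, 20% and 30% of children are dropped. If each annual visit were missed independently by 3%, 5% or 10% (assumed), 294 × (1 − q)³ leaves 268, 252 or 214 complete children, all above 186.

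**3. Reserve in Aim 3.** 294 − 267 = 27 children, or 9.2%. At exactly 10% dropped, 264.6 remain (88.2 per group) and power is 80.1%. Adding incomplete children (rates assumed):

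| Lost | Incomplete among the rest | Complete | Power |
|---|---|---|---|
| 10% | 2% | 259 | 79.2% |
| 10% | 5% | 251 | 77.9% |
| 10% | 10% | 238 | 75.5% |
| 2% | 5% | 274 | 81.5% |

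**4. How single readings accumulate in Aim 3.** Assume change from baseline to one follow-up visit, all ten locations in one model, and independent failures. Each child then needs 10 × 2 = 20 readings, and the complete share is (1 − q)^20. Start from 88.2 per group after 10% loss, and round down.

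| q per reading | Complete | Per group | Power |
|---|---|---|---|
| 0.5% | 90% | 79 | 75% |
| 1% | 82% | 72 | 71% |
| 2% | 67% | 58 | 61% |

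**5. Sensitivity.** With 2% lost instead of 10%, as in the 98% retention that Chapter 5 cites, q = 0.1%, 0.5% and 1% give power of about 83%, 79% and 75%. By meridian at q = 1% with 10% lost, the horizontal model needs 12 readings (0.99^12 = 89% complete, 78 per group, about 75%). The vertical model needs 8 (0.99^8 = 92%, 81 per group, about 76%).

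**The case against.** **Listwise deletion is inferred.** The name of the model does not fix how it is fitted, a mixed model would be compatible with it, and Chapter 31 leaves a detailed analysis plan to be developed with the Data Coordinating Center for each approved paper. This is fair: deletion is the usual fit, not a stated rule. But that later plan is tied to a paper proposal and is not dated relative to the data, so the choice stays open for the primary comparison.

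**A reader might infer that the 10% allowance fails to cover the actual loss.** The documents do not show this. They give no rate of missing readings, and the retention they cite (98%, 100%, above 90%) could leave room inside the 10%.

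**A reader might infer that Aim 1 is underpowered, or that Visit-9-only children erode Aim 3.** Neither follows. Aim 1 has a wide margin. A Visit-9-only child may be complete for Aim 3 if change runs from baseline to Visit 9. A child who stops after Visit 7 and returns for Visit 9 has all three annual values for Aim 1.

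**A reader might infer a known bias toward adherent children.** The documents do not say that Visit-9-only children have usually stopped lens wear. The Crossovers section has children who decline lenses asked about resuming at each follow-up visit, so stopping lenses is not the same as stopping visits. The direction and size of any bias are unknown.

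**The evidence of failed locations is indirect.** The rule in Chapter 21 concerns another instrument and fewer than five valid readings, not an empty location. Lifting the lid in down gaze (Chapter 22) is a way to obtain the reading. Failures probably cluster within children, so independence overstates the loss. The 40° positions exist only horizontally, so a single ten-location model is itself an assumption. All of this limits the illustration but does not supply a missing-data rule.

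**Conclusion.** The point holds in a limited form. The plan names an analysis that ordinarily uses complete cases, and it says nothing about missing visits, missing locations or who is analysed.

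For Aim 1 the consequence is possible selection in the primary comparison. It is not a loss of power, and its size cannot be estimated from the documents.

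For Aim 3 the firm result is the threshold: more than 27 of 294 children dropped, for any reason, takes complete cases below 267. The illustrative powers of 75%, 71% and 61% rest on assumed rates, 10% loss, 20 readings per child and independent failures. They show how quickly small gaps add up and are not a forecast. With low loss and very rare failures the allowance suffices.

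**What to change.** For both aims, specify a likelihood-based linear mixed model on all available visits and locations, with children analysed in the arm to which they were randomised. State the analysis set as every randomised child with at least one post-baseline reading. For Aim 3, enter locations as repeated records within child, so that an unobtainable location costs one record and not the child. A Visit-9-only child then contributes the Year 3 value to Aim 1, and a later drop-out contributes the values obtained before leaving.

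The cost is a missing-at-random assumption, which should be stated, and a small amount of analysis work. No additional children, visits or measurements are needed.
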